1 DESCRIPTION OF OBJECTIVES AND ENDPOINTS

1.1 Primary Objective and Endpoint

The primary objective of this study is to evaluate the efficacy of monthly doses of aducanumab in slowing cognitive and functional impairment as measured by changes in the Clinical Dementia Rating-Sum of Boxes (CDR-SB) score as compared with placebo in subjects with early Alzheimer's Disease (AD).

The primary endpoint that relates to this objective is change from baseline in CDR-SB score at Week 78.

1.2 Secondary Objectives and Endpoints

The secondary objectives of this study are:

- To assess the effect of monthly doses of aducanumab as compared with placebo on clinical progression as measured by the Mini-Mental State Examination (MMSE).
- To assess the effect of monthly doses of aducanumab as compared with placebo on clinical progression as measured by Alzheimer's Disease Assessment Scale-Cognitive Subscales (13 items) [ADAS-Cog 13].
- To assess the effect of monthly doses of aducanumab as compared with placebo on clinical progression as measured by Alzheimer's Disease Cooperative Study-Activities of Daily Living Inventory (Mild Cognitive Impairment version) [ADCS-ADL-MCI].

The secondary endpoints are:

- o Change from baseline in MMSE score at Week 78.
- o Change from baseline in ADAS-Cog 13 score at Week 78.
- o Change from baseline in ADCS-ADL-MCI score at Week 78.

1.3 Tertiary Objectives and Endpoints

1.3.1 Tertiary Objectives

Safety and Tolerability

- To assess the safety and tolerability of monthly doses of aducanumab.
- To assess the immunogenicity of aducanumab.

Biomarker/Efficacy/Quality of Life

Final V1.0

- To assess the effect of aducanumab on cerebral amyloid plaque content as measured by amyloid positron emission tomography (PET) imaging (in a subset of approximately 400 subjects).
- To assess the effect of aducanumab on behavior as measured by the Neuropsychiatric Inventory-10 (NPI-10).
- To assess the effect of aducanumab on subject health status, measured by EuroQol health status measures (EQ-5D [informant-rated and subject self-reported]).
- To assess the effect of aducanumab on subject self-reported cognitive function, measured by the modified Perceived Deficits Questionnaire-20 (mPDQ-20).
- To assess the correlation between primary endpoint and cerebral amyloid plaque content as measured by PET imaging.

Pharmacokinetics

• To collect and characterize the pharmacokinetic (PK) parameters of aducanumab in serum

1.3.2 Tertiary Endpoints

Safety and Tolerability

- Incidence of all adverse events (AEs) and serious adverse events (SAEs).
- Brain magnetic resonance imaging (MRI) findings including incidence of amyloid related imaging abnormality-edema (ARIA-E) and amyloid related imaging abnormality-hemorrhage or superficial siderosis (ARIA-H).
- Clinical laboratory shifts in reported values.
- Clinically significant changes in vital sign measurements and electrocardiograms (ECGs).
- Incidence of anti-aducanumab antibodies in serum.

Biomarkers/Efficacy/Quality of Life

- Change from baseline in amyloid PET signal at Week 26 (in a subset of sites and subjects).
- Change from baseline in amyloid PET signal at Week 78 (in a subset of sites and subjects).
- Change from baseline in NPI-10 score at Week 78.
- Change from baseline in subject-self-reported EQ-5D index score at Week 78.
- Change from baseline in informant-rated subject EQ-5D index score at Week 78.
- Change from baseline in mPDQ-20 at Week 78.
- Correlation between the primary endpoint and cerebral amyloid plaque content as measured by PET imaging over time.

Pharmacokinetics:

[figure not shown]

Final V1.0

• Serum concentrations and PK parameters of aducanumab.

1.4 Additional Exploratory Objectives and Endpoints

1.4.1 Additional Exploratory Objectives

CONFIDENTIAL

2 STUDY DESIGN

2.1 Study Overview

Study 221AD301 (ENGAGE) is a multicenter, randomized, double-blind, placebo-controlled, parallel-group study in subjects with early AD, including mild cognitive impairment (MCI) due to AD and a subset of mild AD, followed by an optional dose-blinded long-term extension (LTE) period of up to 5 years. Approximately 1605 subjects will be enrolled across approximately 150 centers globally. The primary study objective is to evaluate the efficacy of monthly doses of aducanumab on the CDR-SB relative to placebo. Secondary objectives include assessment of the effect of monthly doses of aducanumab on clinical progression as compared to placebo. The safety of monthly doses of aducanumab will also be evaluated.

Table 1: Dosing Scheme for Aducanumab by Treatment Group and ApoE ε4 Carrier Status: Placebo-Controlled Period

Dose (every 4 weeks)			2	3	4	5	6	7 to 20
Treatment Group Stratified by ApoE Status ²]	Dose (m	g/kg)		
High Dose - ApoE ε4 (+)		1	1	3	3	6	6	10 ¹
	High Dose - ApoE ε4 (-)	1	1	3	3	6	6	10
Low Dose	Low Dose - ApoE ε4 (+)	1	1	3	3	3	3	3
	Low Dose - ApoE ε4 (-)	1	1	3	3	3	3	6
Placebo	Placebo - ApoE ε4 (+)	saline						
	Placebo - ApoE ε4 (-)	saline						

¹⁰ mg/kg is the target dose for all ApoE ε4 carriers assigned to the aducanumab high-dose group. Subjects enrolled under protocol versions 1-3 and assigned to the previous high-dose of 6 mg/kg will be titrated to 10 mg/kg upon receipt of at least 2 doses at 6 mg/kg.

Subjects will be randomized in a 1:1:1 ratio to 1 of the 3 treatment groups: aducanumab high dose, aducanumab low dose and placebo, with stratification based upon their apolipoprotein E4 (ApoE &4) carrier status (carrier/non-carrier) and site. During the placebo-controlled period, subjects will receive infusions of aducanumab or placebo approximately every 4 weeks for approximately 18 months (a total of 20 doses). Dose levels may be different in the same treatment group based upon subjects' ApoE &4 carrier status, and specifically, ApoE &4

² ApoE ε4 status recorded in the Interactive Voice/Web Response System (IXRS).

Final V1.0

carriers will receive placebo, aducanumab 3 mg/kg, or aducanumab 10 mg/kg whereas ApoE ε 4 non-carriers will receive placebo, aducanumab 6 mg/kg, or aducanumab 10 mg/kg. Aducanumab will be titrated for up to 6 doses prior to reaching the target dose as shown in Table 1 and Figure 1. Note: As of Protocol Version 4, 10 mg/kg is the target dose for all ApoE ε 4 carriers in the high-dose group. ApoE ε 4 carriers who were randomized to the high dose group when the target dose was 6 mg/kg (under protocol versions prior to Version 4) must have received 2 or more doses at 6 mg/kg prior to being titrated up to 10 mg/kg.

At the end of the double-blind, placebo-controlled treatment period, subjects who meet the extension entry criteria may enter a long-term safety and efficacy extension period, with all subjects receiving aducanumab approximately every 4 weeks (up to a total of 65 doses over 5 years). The treatment group for the LTE period will be assigned at the same time as the randomization for the placebo-controlled period, regardless of whether a subject entering the LTE period or not. Subjects who are assigned to the placebo group during the placebo-controlled period will be assigned to 1 of 2 active treatment groups in a 1:1 ratio (aducanumab low dose: aducanumab high dose) and randomization will be stratified by their ApoE \(\epsilon\) 4 carrier status; for those who enter the LTE period, aducanumab will be titrated for up to 6 doses prior to reaching the target dose following the same schedule described for the placebo-controlled period. Subjects who are assigned to either aducanumab low dose or aducanumab high dose group in the placebo-controlled period will continue in the same treatment group for the LTE period; those who enter the LTE period will maintain the dosing scheme outlined in the protocol at the time of transition from the placebo-controlled period to the LTE period (e.g. subjects who are on stable dosing in the placebo-controlled period will continue on the same dose, subjects who are on a titration regimen during the transition will continue to titrate into the LTE period, and ApoE & carrier subjects who are enrolled in the LTE and randomized to the high-dose group prior to implementation of version 4 of the protocol will be allowed to titrate to 10 mg/kg).

[figure not shown]
Individual dose adjustments may be implemented in subjects who develop amyloid related imaging abnormalities (ARIA). See Protocol Section 7.2.1.

The total duration of study participation for each subject only participating in the placebo-controlled period of the study will be up to approximately 102 weeks, including a series of Screening visits within 8 weeks before administration of the first dose, a 76-week placebo-controlled treatment period, and a safety follow-up (FU) period of approximately 18 weeks after the final dose. The total duration of study participation for each subject participating in the placebo-controlled period and the LTE period will vary and be up to approximately 362 weeks, including a series of Screening visits within 8 weeks before administration of the first dose, a 76-week placebo-controlled treatment period, a 4-week FU period, a 256-week aducanumab dose-blind treatment period, and a safety FU period of approximately 18 weeks after the final dose.

Investigators, study site staff (except for the designated unblinded pharmacist/technician), and study subjects will be blinded to the subjects' randomized treatment assignment for the placebo-controlled period. During the LTE period, investigators and subjects will remain blinded to the treatment assignment in the placebo-controlled period and the aducanumab dose for the LTE period.

2.2 Study Schematic

Figure 1: Study Design

ApoE $\varepsilon 4$ +/- = apolipoprotein E4 positive/negative; FU = follow-up; P = placebo; R = randomization date.

*Subjects who are assigned to placebo during the placebo-controlled period are randomized in a 1:1 ratio to high and low dose aducanumab treatment (stratified by their ApoE & carrier status) for the long-term extension period on Study Day 1.

CONFIDENTIAL

The information contained herein may not be used, disclosed, or published without the written consent of Biogen MA Inc.

2.3 Schedule of Events

See Protocol Section 4.2.

3 SAMPLE SIZE JUSTIFICATION

The study's sample size is based, in part, on results from a protocol-specified interim analysis from Study 221AD103 which included 1 year data from 1, 3 and 10 mg/kg treatment groups.

A sample size of 450 subjects per treatment group (1350 in total) was planned to have approximately 90% power to detect a true mean difference of 0.5 in change from baseline CDR-SB at Week 78 between the 2 treatment groups. This power calculation was based on a 2-sided t-test assuming equal variance with a final significance level of 0.05, a standard deviation (SD) of 1.92 and a drop-out rate of 30%. The SD estimate of 1.92 for Week 78 reflected a 39% increase over the SD from the protocol-specified interim analysis of 1-year data.

The assumed true mean difference of 0.5 between the 2 treatment groups represents an approximately 25% reduction in the placebo mean change from baseline at Week 78 if the placebo mean change is estimated to be 2.

As defined in the protocol, the sample size for this study (and for the identically designed Study 221AD302) was reassessed in a blinded manner in November 2017 (approximately 3 months before enrollment completion and with about 10.6% of the data available on the primary endpoint from Studies 221AD301 and 221AD302 combined). At this timepoint, the SD of the primary endpoint was estimated based on the pooled blinded data from two studies using a modified version of Gould-Shih simple-adjustment one sample variance (Zucker et al. 1999):

$$s_{adj}^2 = s_{os}^2 - \frac{2N}{9(N-1)}\delta^2,$$

where N denotes the number of subjects included in the analysis for blinded sample size reestimation (subjects with both baseline and Week 78 CDR-SB available at the time of sample size re-estimation), δ is the assumed true treatment effect (same treatment effect assumed for both the high dose group and low dose group in this analysis), and s_{os}^2 is the unadjusted one sample variance of the primary endpoint estimate from the pooled blinded data.

As a result of this analysis, the sample size has been increased from 1350 to 1605 (450 to 535 per treatment group) to assure adequate power for detecting a mean treatment effect of 0.5.

4 STATISTICAL ANALYSIS METHODS

4.1 General Considerations

This statistical analysis plan (SAP) only covers the analyses for the primary, secondary and tertiary objectives for the placebo-controlled portion of the study. Hereafter, the placebo-controlled portion of the study will be referred to as "the study" in the rest of this SAP (e.g.,

Final V1.0

completion of the study means completion of the placebo-controlled portion). A separate SAP will be prepared for the analyses of the LTE period and integrated analyses across both portions of the study. The analyses of additional exploratory endpoints will be documented separately.

Summary tables will be presented using descriptive summary statistics. For continuous variables, summary statistics will generally include: number of subjects with data, mean, standard deviation, median, 25% percentile, 75% percentile, minimum and maximum. For categorical variables, this will generally include: number of subjects randomized or dosed, number with data, and the percent of those with data in each category.

There are two types of analysis displays for tables: by treatment group (analysis display A in Appendix 6.1) and by treatment group stratified by ApoE status (analysis display B in Appendix 6.1; here ApoE status refers to the status recorded in IXRS [see Table 1 for correspondence between treatment groups and treatment groups stratified by ApoE status]). The analysis display for each analysis will be defined in each section. All the listings will be presented by treatment group stratified by ApoE status, unless otherwise specified.

Unless otherwise specified, baseline value is defined as the most recent non-missing measurement collected prior to the first dose. Change from baseline will be defined as post-baseline value minus baseline value.

Unless stated otherwise, all statistical tests will be 2-sided with statistical significance level of 0.05.

The statistical software, SAS® will be used for all summaries and analyses.

4.1.1 Analysis Population

- Intent-to-treat (ITT) population: The Intent-to-treat population is defined as all randomized subjects who received at least one dose of study treatment (aducanumab or placebo).
- Per-protocol (PP) population:

The per-protocol population is defined as all subjects in the ITT population and also

- o had no violations of the following inclusion criteria:
 - Must have at least 6 years of education or work experience to exclude mental deficits other than MCI or mild AD;
 - Must have a positive amyloid PET scan;
 - Must have:
 - A CDR-Global Score of 0.5;
 - A Repeatable Battery for Assessment of Neuropsychological Status (RBANS) score of 85 or lower indicative of objective cognitive impairment (based upon the Delayed Memory Index score);
 - An MMSE score between 24 and 30 (inclusive).
- o had at least 14 infusions.
- o did not make any change to concomitant AD symptomatic medications during the study.

Final V1.0

- ¹⁸F-florbetapir amyloid PET analysis population:
 - The ¹⁸F-florbetapir amyloid PET analysis population is defined as all randomized subjects who received at least one dose of study treatment (aducanumab or placebo), used ¹⁸F-florbetapir ligand for amyloid PET scan, and had an evaluable baseline amyloid PET SUVR value for the composite region-of-interest using cerebellum as the reference region.
- ¹⁸F-flutemetamol amyloid PET analysis population (applicable only to Japan): The ¹⁸F-flutemetamol amyloid PET analysis population is defined as all randomized subjects who received at least one dose of study treatment (aducanumab or placebo), used ¹⁸F-flutemetamol ligand for amyloid PET scan, and had an evaluable baseline amyloid PET SUVR value for the composite region-of-interest using cerebellum as the reference region.

• Safety population:

The safety population is defined as all randomized subjects who received at least one dose of study treatment (aducanumab or placebo). It is the same population as the ITT population.

• Safety MRI population:

The safety MRI population is defined as all randomized subjects who received at least one dose of study treatment (aducanumab or placebo) and had at least one post-baseline MRI assessment.

• PK analysis population:

The PK analysis population is defined as all randomized subjects who received at least one dose of study treatment (aducanumab or placebo) and had at least one measurable aducanumab concentration in serum.

• Immunogenicity population:

The analysis population for immunogenicity is defined as all randomized subjects who received at least one dose of study treatment (aducanumab or placebo) and had at least one post-dose sample evaluable for immunogenicity.

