^{*} Analysis excludes data collected after the following intercurrent events: (1) premature discontinuation of the study treatment and (2) any change to concomitant AD symptomatic medications during the study. All other analyses will include data collected after intercurrent events [ICH E9 (R1) Addendum 2017].

Visit windows for mapping efficacy endpoint

For efficacy data that are summarized or analyzed by visit, data collected on all scheduled visits and all unscheduled visits will be mapped to an appropriate analysis visit using the windowing scheme shown in Table 3. If there are 2 or more assessments available in the same analysis window for a subject, the assessment that is closest to the target visit day will be used for analysis. If there are 2 or more assessments in the same analysis window with the same distance from the target visit day, the later assessment will be used.

Table 3. Visit Windows for Efficacy Endpoints

Target visit day	Analysis visit window
1	Most recent non-missing pre-dose value
183	[92, 266]
351	[267, 448]
547	[449, the end day of the placebo-controlled period *]
	1 183 351

^{*} The end day of the placebo-controlled period is the last day before the first infusion in LTE for subjects who enter LTE, and is the last day in study for subjects who do not enter LTE.

Handling of missing items for scales

If any of the individual items for the primary and secondary endpoints is missing, the total score of the corresponding endpoint will be imputed by prorating the observed scores [van Ginkel 2010].

For ADAS-Cog13, if 3 or fewer of 13 items (<25%) are missing, the total score will be imputed by the following algorithm: Total score = total score from the completed items * [maximum total score (=85) / maximum total score for the completed items]. The imputed number will be rounded up to the nearest integer. If more than 3 items are missing, the total score of ADAS-Cog 13 at that visit will be considered missing.

For ADCS-ADL-MCI, if 4 or fewer of 18 items (<25%) are missing, the total score will be imputed by a similar algorithm as that for ADAS-Cog 13. The imputed number will be

Final V1.0

rounded up to the nearest integer. If more than 4 items are missing, the total score for ADCS-ADL-MCI at that visit will be considered missing.

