4.3.2.3 Supplementary analysis

4.3.2.3.1 Censoring after intercurrent events

The primary analysis (Section 4.3.2.1) will be repeated with the data censored after any of the following intercurrent events (if multiple events occur to the same subject, data after the earliest event will be censored):

- o premature discontinuation of the study treatment;
- o any change to concomitant AD symptomatic medications during the study.

The estimate of this analysis reflects the treatment effect of aducanumab if the drug is taken as directed.

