4.5.2 Clinical Adverse Events

Treatment-emergent AEs (TEAEs)

All AEs will be analyzed based on the principle of treatment emergence. A treatment-emergent AE was defined as an AE that started or worsened after the start of first infusion of study treatment.

To define treatment emergence for AEs with missing start or stop date or time the following additional criteria will be used:

- if both the start and stop dates for a particular AE are missing, then that AE is considered treatment emergent;
- if the start date for a particular AE is missing and the stop date/time falls after the first dose date/time, then that AE is considered treatment emergent;
- if the start date for a particular AE was the same as the first dose date, and the start time was missing, then that event is considered treatment emergent.

For AEs with a partial start date, the year/month of the event date will be compared to that of the first dosing date to determine whether the event is treatment emergent.

In addition, SAEs that occurred since a subject was screened in the study and prior to the first infusion of study treatment, which by definition are not treatment-emergent, will be analyzed separately.

Only TEAEs will be included in the AE tables, unless otherwise specified. Listings of AEs will include all events, whether treatment-emergent or not.

As specified in the protocol, subjects were expected to return to the study site for an End of Study visit 18 weeks after the last administration of study treatment. However, some subjects may elect to continue study participation on a modified schedule after discontinuing treatment, possibly in substantial excess of 18 weeks. For most general AE summaries, AEs

Final V1.0

with an onset more than 18 weeks after the last dose will be excluded (will specify in the footnote of the specific table). For incidence rate analyses excluding AEs more than 18 weeks after the last dose, the "last day on study" in follow-up time calculation will be replaced with "18 weeks after last dose or last day on study, whichever earlier". Summaries of deaths and AEs leading to study withdrawal, and other selected analyses will include all AEs regardless of the time since the last dose. Listings will include all AEs, unless otherwise specified.

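### The per-protocol rule on AD-medication change has no cut-off at the endpoint, so a change made after a subject's last analysed assessment removes all of that subject's data from the supplementary per-protocol analyses

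*SAP*

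**What the plan says.** The third per-protocol criterion in SAP section 4.1.1 is that the subject "did not make any change to concomitant AD symptomatic medications during the study". It works on the whole subject and gives no end date other than the study itself.

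The length of the study follows from other sections:

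- Section 4.1 (General Considerations) states that "the placebo-controlled portion of the study will be referred to as 'the study' in the rest of this SAP".
- The footnote to Table 3 (section 4.3.1) closes that period as follows: "The end day of the placebo-controlled period is the last day before the first infusion in LTE for subjects who enter LTE". For everyone else the closing day "is the last day in study for subjects who do not enter LTE".
- Section 2.1 describes participation in the placebo-controlled period alone as including "a 76-week placebo-controlled treatment period, and a safety follow-up (FU) period of approximately 18 weeks after the final dose". Section 4.5.2 agrees: "subjects were expected to return to the study site for an End of Study visit 18 weeks after the last administration of study treatment". Subjects who go on to the LTE have a 4-week follow-up before it starts.

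The per-protocol analysis (4.3.2.3.2) reruns the primary MMRM on this population with no date limit, and 4.3.3.4 repeats it for the three secondary endpoints. The last timepoint in all of these models is Week 78. The censoring analysis in 4.3.2.3.1 reacts to the same event, "any change to concomitant AD symptomatic medications during the study", but drops only the data that follow it.

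**The concern.** A per-protocol population should screen out departures that could have affected the outcome being analysed. A symptomatic drug started during safety follow-up, after the last score used in the model, is not such a departure. As written, it still removes every score from that subject.

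The period in which this can happen also differs by a post-randomisation choice. It is longer for subjects who decline the LTE than for those who enter it. Both LTE entry and later prescribing may be related to how the subject has fared, so the rule adds a selection step that has nothing to do with adherence before the endpoint. At stake are some precision and a possible small distortion in the per-protocol estimates for CDR-SB, MMSE, ADAS-Cog 13 and ADCS-ADL-MCI.

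**Working it through.** **1. Check the timeline against the plan's own totals (section 2.1).**
- Placebo-controlled period only: 8 (screening) + 76 (treatment) + 18 (follow-up) = 102 weeks, as stated.
- With the LTE: 8 + 76 + 4 + 256 + 18 = 362 weeks, as stated.

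**2. Time after Week 78 in which a change still excludes.**
- Not entering the LTE, final dose at Week 76: 76 + 18 = Week 94, and 94 − 78 = 16 weeks. In days, the Week 76 dose is day 533; 533 + 126 = 659, against the Week 78 target day of 547.
- Entering the LTE: 76 + 4 = Week 80, and 80 − 78 = 2 weeks (about day 561 against day 547).
- Ratio per subject: 16/2 = 8.

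**3. How many subjects are lost.** The SAP gives neither a medication-change rate nor LTE uptake, so both are assumed. Let r be the proportion changing medication over 78 weeks at a constant rate h = −ln(1 − r)/78. The chance of a change in a window of w weeks is 1 − exp(−h·w). With a proportion p not entering the LTE, the overall loss is p·P16 + (1 − p)·P2.

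| r over 78 weeks | P16 (non-entrant) | P2 (entrant) | Loss at p = 5% | p = 20% | p = 50% |
|---|---|---|---|---|---|
| 10% | 2.1% | 0.3% | 0.4% | 0.6% | 1.2% |
| 20% | 4.5% | 0.6% | 0.8% | 1.4% | 2.5% |
| 30% | 7.1% | 0.9% | 1.2% | 2.1% | 4.0% |

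The range is about 0.4% to 4.0% of otherwise eligible subjects.

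**4. Who they are.** At equal weekly rates, and with windows short enough to treat the chance as proportional to their length, non-entrants make up 16p/(16p + 2(1 − p)) of those lost. That exceeds one half only when p is above 2/18 = 11.1%. It is 30% at p = 5%, 67% at p = 20% and 89% at p = 50%.

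**5. Effect on the estimate if changes follow decline.** Section 3 supplies a difference of 0.5, an SD of 1.92 and a placebo mean change of 2, so the two arms are taken as normal with means 2 and 1.5. The probability of exclusion is logistic in the CDR-SB change, with assumed log-odds of 0.3 or 0.6 per point and the intercept set to give the stated placebo fraction. The difference in means among those kept was obtained by numerical integration.

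| Placebo subjects excluded | Log-odds 0.3 | Log-odds 0.6 |
|---|---|---|
| 0.4% | 0.499 | 0.498 |
| 4.0% | 0.494 | 0.481 |

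The largest shrinkage is 0.50 − 0.481 = 0.019. This compares raw Week 78 means; it does not refit the MMRM.

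**The case against.** The strongest reply is that nothing decisional depends on this. Table 2 labels the per-protocol analysis supplementary, section 4.3.1 gives supplementary analyses no multiplicity adjustment, and the primary analysis is ITT on all observed data. If changes follow decline, the distortion runs toward no difference, so it would not create an apparent benefit. All of that stands, and it is why the point is minor.

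One could also say that the Table 3 footnote was written for visit windows and not for the per-protocol rule. But it is how the SAP defines the end of the placebo-controlled period, section 4.1 ties the study to that period, and nothing in 4.1.1 or 4.3.2.3.2 sets an earlier limit.

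A reader might infer three stronger things that the document does not support:

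- *That whole-subject exclusion for a change at, say, Week 60 is also an error.* It is a conventional per-protocol choice, and the other criteria in 4.1.1 work the same way. Section 4.3.2.3.1 already supplies the version that keeps earlier data, so converting the per-protocol rule to censoring would largely duplicate it.
- *That the treatment difference drops materially, for example to 0.42.* Such a figure needs about 30% of placebo subjects excluded for decline at any time (log-odds 0.6). It does not describe changes after the endpoint.
- *That mostly non-entrants are lost.* The eightfold window is secure per subject. The head count needs non-entry above about 11%, and the SAP states no uptake.

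**Conclusion.** The defect holds on the SAP's own definitions. The per-protocol medication criterion extends past the endpoint, by up to about 16 weeks for a non-entrant dosed to Week 76 and by about 2 weeks for an LTE entrant. A change after the last analysed assessment then removes scores it could not have affected.

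Its size is small: about 0.4-4% of otherwise eligible subjects, and a shrinkage of about 0.02 or less on a difference of 0.5. These figures rest on assumed change rates (10-30% over 78 weeks, constant), assumed LTE non-entry (5-50%) and, for the shrinkage, an assumed link between change and decline. The criterion covers changes for any reason, so that link may be weaker.

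Two limits apply. The 16 weeks presume a final dose at about Week 76; a subject who stopped after 14 or more infusions may have a different window, and not all of that subject's scores are on treatment. Also, the Week 78 analysis window stays open to the end of the period, so a change after nominal Week 78 can precede a late assessment and still be relevant. What matters is the date of the analysed assessment, not the nominal week.

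**What to change.** In section 4.1.1, keep the AD-medication criterion but replace its open-ended time reference with a cut-off: no change on or before the date of the subject's analysed Week 78 efficacy assessment or, if there is none, the last analysed efficacy assessment. The fallback covers a subject with 14 or more infusions and no Week 78 score. Leave whole-subject exclusion for earlier changes as it is, and leave 4.3.2.3.1 unchanged.

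The cost is one clause and one extra date derivation. If the scales at a visit were done on different days, the derivation must name which date counts, so that one per-protocol population still serves all four endpoints.
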